### **10.8.3. Assessment of Response Criteria**

Evidence supports that cancer-associated IDH mutations block normal cellular differentiation and promote tumorigenesis via the abnormal production of 2-HG, a potential oncometabolite (Figure 3). AG-221 may produce antitumor effects by reversing the differentiation block induced by the IDH2 mutations and promoting appropriate cellular differentiation.

The response pattern seen with such mechanism of action may extend beyond the typical time course of responses seen with cytotoxic agents, and can generate a clinical response after an initial increase in the number of immature monocytes or blast cells, and increase in cellularity in the bone marrow, onset of cytopenia after initial rise in platelets, or appearance of differentiation-like syndrome.

Standard assessment criteria developed based on the experience from the cytotoxic chemotherapeutic agents may not provide a complete and accurate response assessment for this novel class of IDH2 inhibitors. Therefore, in the setting where a subject's assessment shows signs similar to progression within the first 2 cycles, caution should be exercised in discontinuing study drug, and a discussion with the Medical Monitor is required, especially in situations where the subject's clinical condition is stable as supported by, but limited to, absence of signs and symptoms of rapid deterioration indicating disease progression and/or general condition is stable or improving.

**Note** that for subjects enrolled in the Phase 1 portion of the trial, the C1D15 bone marrow evaluation should not be used to determine study treatment continuation status in any subject.

Subjects who experience progression of disease (PD) per the applicable response criteria should have assessment of the disease repeated 28 days later in order to confirm PD with option of continuing treatment as described above while awaiting for confirmation. If repeat evaluation confirms PD, subjects will discontinue study treatment and proceed to the survival follow-up phase (see Table 6 for general guidance).

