All subjects are to be followed for survival status follow up every 3 months until death, withdrawal of consent, or end of study for survival.

56-Day transfusion independence rate: The rate of subjects who have been transfusion free for at least 56 consecutive days post baseline during treatment exposure period. Sensitivity analyses will be conducted for all duration of response/remission, time to response/remission, and EFS endpoints in which subjects who go on to receive bone marrow transplantation will be censored at the time of transplantation.

All time to event endpoints will be estimated using Kaplan-Meier methods. Point estimates and 95% confidence intervals will be provided where appropriate. Estimates of the median and other quantiles, as well as individual time points (e.g., 3-month, 6-month, and 12-month rates) will be produced. Additional details of the censoring rules will be specified in the Statistical Analysis Plan. Other measures of clinical activity will be evaluated including summaries of transfusion requirements and infection rates. Descriptive statistics will be used.

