10.3.1.4. Duration of Response

Among subjects who have a response of CR, CRi, CRp, PR, or mCR/MLFS by investigator assessment, DOR will be calculated as the date of the first documented response to the date of the first documented disease relapse, progression or death due to any cause, whichever occurs first. Subjects without relapse, progressive disease, or death due to any cause will be censored at the date of the last adequate response assessment.

Table 3: Censoring Rules for Duration of Response

End Date for Duration of Response	Censored (Y,N)	Scenarios
The earliest of death date, relapse date, and progression date	N	A subject has less than 2 consecutive missing response assessments prior to a documented death, relapse, or progression which is before any subsequent anti-cancer therapy.
The last adequate response assessment date before missing assessments	Y	A subject has 2 or more consecutive missing response assessments prior to a documented death, relapse, or progression.
The last adequate assessment date	Y	If a subject did not die, did not relapse or progression, and did not receive any subsequent anti-cancer therapy.
The last adequate assessment date on or prior to the start of subsequent anti-cancer therapy	Y	If a subject did not die, did not relapse or progression on or prior to subsequent anti-cancer therapy.
The last adequate assessment date on or prior to the start of subsequent AML therapy	Y	If a subject died, relapsed, or had disease progression after receiving subsequent anti-cancer therapy.
1) If response assessment after a single documented progressive disease /relapse shows response including CR, CRi, CRp, PR, mCR/MLFS, the relapse/progression before documented response is considered as NE. 2) Subsequent anti-cancer therapy in this table excludes HSCT.		

DOR will be summarized primarily based on investigator assessment. The DOR will be analyzed using KM methods and KM curves. The 25th percentile, median and 75th percentile of the response duration with 2-sided 95% CI will be provided for overall responders in the FAS for Part 1 Expansion, the combined Phase 1, Phase 2, and the combined Phase 1/2 as described in items 2 to 5 of [Section 5.1](#). KM estimates at 3, 6, 9 and 12 months will be provided at individual time points. Due to the limited sample size of each total daily dose group, DOR will not be analyzed for Phase 1 dose escalation.

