The sensitivity analyses for DOR in overall responders regarding censoring rules will be conducted for the combined Phase 1, Phase 2, and the combined Phase 1/2:

- Subjects who undergo HSCT will be censored at the last adequate assessment prior to HSCT;
- Subjects with 2 or more consecutive missing response assessments prior to an event (death, relapse or disease progression) and/or subjects with subsequent anti-cancer therapies prior to an event will be considered as events at the event date by ignoring the missing assessments and subsequent anti-cancer therapies

In addition, a sensitivity analysis for the confirmed progression will be performed to examine the impact of unreliable progressive disease assessment where a single documented relapse or progression immediately followed by a response will be considered as the first relapse/progression.

The DOR will be analyzed based on the IRAC adjudicated response to support the primary results by investigator assessment. Sensitivity analyses regarding censoring rules will be performed for IRAC DOR.

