10.3.2.1. Event-Free Survival

Event-free survival is defined as the interval from the date of the first dose to the date of documented relapse, progression, or death due to any cause, whichever occurs first. Subjects without an EFS event will be censored according to the rules in [Table 3](#). Subjects who only have a baseline record will be censored at date of the first dose.

The analysis methods for EFS are similar to those for DOR. The KM method will be used to estimate the EFS probabilities at 3, 6, 9 and 12 months. The EFS based on IRAC assessment will also be analyzed for Phase 2 R/R AML subjects.

EFS will be analyzed in the FAS for Part 1 Expansion, the combined Phase 1, Phase 2, and the combined Phase 1/2. Due to the limited sample size of each total daily dose group, EFS will not be analyzed for Phase 1 dose escalation.

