10.3.2.2. Duration of Complete Response

Among subjects who achieve a CR, DOCR is defined as the time from the date of the first documented CR to the earlier date of documented disease relapse or death due to any cause, using similar censoring as in [Table 3](#).

Kaplan-Meier methods will be used to estimate DOCR in the FAS subjects with CR for Part 1 Expansion, the combined Phase 1, Phase 2, and the combined Phase 1/2. The corresponding KM curves will be provided as well. The DOCR assessed by IRAC will be analyzed to provide supportive evidence.

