10.3.2.3. Duration of CR/CRh

Among subjects who achieve a CR/CRh, DOCR/CRh is defined as the time from the date of the first documented CR or CRh to the earlier date of documented disease relapse or death due to any cause, using similar censoring as in [Table 3](#).

Kaplan-Meier methods will be used to estimate DOCR/CRh in the FAS subjects with CR/CRh for the combined Phase 1, Phase 2, and the combined Phase 1/2. The corresponding KM curves will be provided as well. The DOCR/CRh analyses will be based on IRAC assessments.

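### Does resetting a single relapse or progression to NE when a response follows need its own check for EFS, DOCR and DOCR/CRh, and a dose-increase condition?

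*SAP*

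**What the plan says.** SAP 10.3.1.4 sets the censoring rules for DOR in Table 3. Under its note 1, if an assessment after a single relapse or progression shows CR, CRi, CRp, PR or mCR/MLFS, "the relapse/progression before documented response is considered as NE". The note has no condition on dose, and no row of Table 3 ends or censors follow-up at an AG-221 dose increase.

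The same section then says "The sensitivity analyses for DOR in overall responders regarding censoring rules will be conducted" for the combined Phase 1, Phase 2 and combined Phase 1/2 groups. It adds an analysis in which "a single documented relapse or progression immediately followed by a response will be considered as the first relapse/progression". That analysis undoes note 1.

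The other endpoints refer back:
- EFS (SAP 10.3.2.1) is censored by Table 3, and "The analysis methods for EFS are similar to those for DOR".
- DOCR (SAP 10.3.2.2) runs to "documented disease relapse or death due to any cause, using similar censoring as in" Table 3.
- DOCR/CRh (SAP 10.3.2.3) uses adjudicated (IRAC) responses, and its interval is given as "first documented CR or CRh to the earlier date of documented disease relapse or death due to any cause, using similar censoring as in", where the reference is again to Table 3.

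For transplant, the protocol is broader. Section 12.5.7 says "Sensitivity analyses will be conducted for all duration of response/remission, time to response/remission, and EFS endpoints", with transplanted subjects censored at transplantation.

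**The concern.** Protocol 9.7.2.1 lists evidence of relapse or progression as a reason to raise the AG-221 dose, in Part 1 Expansion and in Phase 2 (100 to 200 mg QD), and does not say that it must be confirmed first. A response regained after a dose increase does not show that the earlier reading was false, yet note 1 would erase that reading.

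Compared with counting the first reading, note 1 can only lengthen a duration or leave it unchanged. Efficacy groups follow the assigned dose (SAP 5.1 and 5.2.1), and the combined Phase 1/2 analysis centres on 100 mg (SAP 10), so remission regained at 200 mg would be credited to 100 mg. With the restoring analysis named only for DOR, a reader of the EFS, DOCR and DOCR/CRh results might not see how much of the duration comes from the reset.

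**Working it through.** **The plan's own figure.** The plan gives none for DOR, EFS, DOCR or DOCR/CRh. The nearest is the response-rate criterion in Protocol 12.1. For 42/125 = 33.6%, the exact 95% limits are the 2.5% point of Beta(42, 84) and the 97.5% point of Beta(43, 83), which are 25.4% and 42.6%, as stated. Note 1 sets end dates for durations and does not enter this calculation.

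**Step 1: note 1 against the response criteria.** The footnote to Protocol Table 7 asks for relapse to be confirmed by two consecutive assessments at least a month apart. Table 8 asks the same for progression, and Protocol 10.8.3 schedules the repeat 28 days later. One reading followed by a response fails that test. Protocol 12.3 counts progression at its first occurrence in subjects treated beyond it. It does not say whether documented means confirmed, but Table 8 dates a progression at its first reading, so 12.3 can be read as fixing the date of a confirmed event. Sections 12.3 and 12.5.7 both leave further censoring detail to the SAP.

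**Step 2: a Phase 2 subject in CR who has a relapse reading.** Marrow is assessed every 28 days through at least Cycle 12 (Protocol 10.8.2), and a dose increase applies to subsequent cycles (Protocol 9.7.2.1). The reading at the start of the next cycle therefore comes before any effect of the increase.

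| Next reading | Consequence |
|---|---|
| Evaluable, not in response | MLFS counts as a response and needs only blasts below 5%, no Auer rods and no extramedullary disease. Apart from an isolated Auer-rod finding, failing it means blasts of 5% or more or extramedullary disease, which is relapse again. The relapse is no longer single, so note 1 does not apply and the event stands. |
| Response | The reset applies, but the increase did not cause it. The response is the very next reading, so it fits the wording of the restoring analysis. |
| Missed or not evaluable | A later response could reset the relapse without fitting that wording. This is the residue. |

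**Step 3: two illustrative paths.** Day of CxD1 = 28(x − 1) + 1; months = days/30.4 (SAP 15.1.1).

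- Path A: response C3, progression C6, stable disease C7, response C8, event C12. DOR is 28 × (6 − 3) = 84 days (2.8 months) by the first reading and 28 × (12 − 3) = 252 days (8.3 months) under note 1. EFS is 28 × 5 = 140 days (4.6 months) against 28 × 11 = 308 days (10.1 months). By Step 2 this fits a PR responder, not a CR subject, so it gives no DOCR contrast.
- Path B: stable disease C2, progression C3, stable disease C4, response C5, relapse C12. EFS is 28 × 2 = 56 days (1.8 months) against 308 days (10.1 months). DOR is 28 × (12 − 5) = 196 days (6.4 months) either way. The C3 reading had already failed confirmation at C4.

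In both paths the stable-disease reading falls at the visit where an increase would start, so the increase cannot explain it.

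**Step 4: size.**
- Shortest deferral per reset, with relapse at t, response at t + s and the next scheduled relapse at t + 2s: 2 × 28 = 56 days (1.84 months) on the Phase 2 schedule, and 2 × 56 = 112 days (3.68 months) on the Part 1 Expansion marrow schedule. Unscheduled assessments could shorten it.
- Shift in a landmark estimate from one reset, without earlier censoring: 1/125 = 0.8 points for EFS; 1/42 = 2.4 points for DOR at the threshold count of responders.
- Shift in the median, by simulation with exponential event times. Each reset event was deferred by 56 days, or by 56 days plus a further exponential time with median 3 or 6 months. For an assumed true median DOR of 6 months, resetting 5%, 10% or 20% of first events gives 6.1 to 6.4, 6.2 to 6.8 or 6.4 to 7.7 months. For an assumed true median EFS of 6 months, resets in 2%, 5% or 10% of subjects give 6.0 to 6.2, 6.1 to 6.4 or 6.2 to 6.8 months.

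**The case for a change.** The strongest case for a change is that the DOR analysis cannot stand in for the others.

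- **EFS.** A progression reading before first response affects EFS only, as Path B shows. The protocol expects such readings: Section 10.8.3 says this mechanism "can generate a clinical response after an initial increase in the number of immature monocytes or blast cells". That passage cuts both ways, since it is also the reason for not treating an early unconfirmed rise as failure. The statement that EFS methods follow DOR arguably carries the restoring analysis across.
- **DOCR and DOCR/CRh.** Only similar censoring is imported, and no restoring analysis is named. In Part 1 Expansion, with marrow every 56 days, relapse, dose increase and response at the next marrow is a single relapse, and the increase has had time to act. This stands, although an earlier confirmatory marrow would narrow it.
- **Wording.** The restoring analysis requires the response to follow *immediately*; note 1 does not. Progression, then stable disease or a missed visit, then response could be reset and not restored. This stands as a looseness.
- **Standing of the endpoints.** Protocol 12.5.7 mentions duration of remission/response in the primary Phase 2 analysis, and SAP Section 13 does not list note 1 as a change. Against that, the synopsis and SAP 4.2.1 make ORR the primary endpoint, and the SAP places DOR among the key secondary endpoints and EFS, DOCR and DOCR/CRh among the others. A delegated censoring detail need not be listed as a change.
- **The 100 mg group.** This comes from analysis by assigned dose, not from note 1. A first response after an increase for lack of PR is counted at 100 mg too.

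**Conclusion.** No change to the plan is needed. Note 1 is a reasonable primary rule because it broadly matches the two-assessment confirmation in the response criteria. Naming the restoring analysis only for the key secondary duration endpoint is a fair trade-off in a single-arm trial whose efficacy analyses are estimates (SAP 10.1). An analyst who wanted the same check for the other endpoints could run it from response dates and the by-subject listing of dose adjustments (SAP 9.6).

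The residue is minor: Part 1 Expansion relapses with a dose increase before the next marrow, missed or non-evaluable visits, early progression readings in EFS, and one adverb that makes the check narrower than the rule. Its frequency is unknown. At a 5% reset rate the medians move by about 0.1 to 0.4 months under the assumptions in Step 4; at 20%, an assumed 6-month median DOR could be reported as up to 7.7 months. Neither the ORR nor its 25% criterion depends on the rule.

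This rests on two readings: that a Phase 2 increase starts with the next cycle, and that documented progression in Protocol 12.3 can be read with the confirmation rule in Tables 7 and 8.

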10.3.1.5. Overall Survival

Overall survival is defined as the time from first dose to the date of death due to any cause. Subjects alive will be censored at the last date known to be alive or a pre-specified data cut-off date, whichever is earlier. The last known alive date is the last non-imputed date of any subject record in the study database. This date may be the last visit date or last contact date that the subject is known to be alive. Subjects who only have a baseline record will be censored at the first dose date.

The OS will be primarily analyzed in the FAS for the Part 1 Expansion, the combined Phase 1, Phase 2, and the combined Phase 1/2 as described in items 2 to 5 of [Section 5.1](#). Due to the limited sample size of each total daily dose group, OS will not be analyzed for Phase 1 dose escalation.

The survival distribution of OS will be estimated using the KM methods. The 25th percentile, median and 75th percentile time with two-sided 95% CI will be provided. KM curves will be provided as well. In addition, KM methods will also be used to estimate the survival probabilities at 3, 6, 9 and 12 months.

Sensitivity analyses for OS will be conducted for the combined Phase 1, Phase 2 and the combined Phase 1/2 where transplanted subjects will be censored at HSCT.

10.3.1.6. 56-Day Transfusion Independence Rate

Subjects who achieved post-baseline 56-day RBC transfusion independence i.e. without RBC transfusion for at least 56 consecutive days post baseline during treatment exposure period will be summarized by baseline RBC transfusion dependence status (Yes vs. No). Subjects with at least one transfusion during the baseline period are considered transfusion dependent at baseline. Baseline period is defined as 28 days before and 28 days after the first dose of treatment for Phase 1, and 56 days before the first dose date for Phase 2.

The post-baseline 56-day Platelet transfusion independence will be analyzed similarly. Subjects who achieved both RBC and Platelet 56-day transfusion independence post baseline during treatment exposure period will be summarized by the status of baseline transfusion dependence i.e. receiving at least one RBC and/or Platelet transfusion during baseline period. Transfusion data will be summarized for the combined Phase 1, Phase 2, and the combined Phase 1/2.

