### **Endpoints**

**Overall response rate (ORR):** ORR is defined as the rate of CR, CRp, mCR [MLFS], CRi, and PR.

**Complete remission rate (CRR):** CRR is defined as the rate of CR.

**Duration of response (DOR):** Among subjects who have a response of CR, CRp, mCR, CRi, or PR, DOR will be calculated as the date of the first occurrence of response to the date of documented disease relapse, progression or death, including subjects that discontinue AG-221 treatment to receive bone marrow transplantation. Kaplan-Meier methods will be used to estimate DOR, and subjects without relapse, progression or death will be censored at the last response assessment date.

**Duration of complete remission (DOCR):** Among subjects who have a response of CR, DOCR will be calculated as the date of the first remission to the date of documented disease relapse or death, including subjects that discontinue AG-221 treatment to receive bone marrow transplantation. Kaplan-Meier methods will be used to estimate DOCR, and subjects without relapse or death will be censored at the last response assessment date.

**Time to response (TTR):** Time to response will be assessed from the date of first dose to the date of first occurrence of response, which includes CR, CRp, mCR/MLFS, CRi, and PR. Subjects without a response will be censored at the date of last response assessment.

**Time to Best Response (TTBR):** Time to best response will be assessed from the date of first dose to the date of first occurrence of best response. Subjects without a response will be censored at the date of last response assessment.

**Time to complete remission (TTCR):** Time to complete remission will be assessed from the date of first dose to the date of first remission (CR). Subjects without a remission will be censored at the date of last response assessment.

**Event-free survival (EFS):** Event-free survival will be calculated from the date of first dose to the date of relapse, progression or death, whichever occurs first. Subjects without an EFS event will be censored at the last response assessment date. Kaplan-Meier methods will be used to estimate EFS, including subjects that discontinue AG-221 treatment to receive bone marrow transplantation.

**Overall survival (OS):** Overall survival is defined as the time from first dose to the date of death. Subjects who are alive at the analysis cutoff date will be censored at the last contact date.

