5. GENERAL STATISTICAL CONSIDERATIONS

5.1. Reporting Conventions

Tabulations will be produced for subject disposition, demographic and baseline disease characteristics, safety, and clinical activity parameters. The study data will be analyzed and reported for efficacy/safety when applicable based on all subjects' data from the Phase 1 dose escalation, the Part 1 Expansion, the combined Phase 1, Phase 2, and the combined Phase 1/2 up to the data cut-off date of 29 July 2019.

Unless specified otherwise, the data will be presented as specified below:

1. In Phase 1 dose escalation, all subjects (combining different malignancy types [overall]) will be utilized. Data will be summarized by total daily dose groups, unless otherwise specified. The total daily dose is defined as the total dose a subject receives during a day based on the assigned or actual dose regimens for efficacy and safety, respectively.
2. In Part 1 Expansion, all subjects (combining different malignancy types) will be utilized and will be grouped into 4 arms (groups):
 - Arm 1: R/R AML and age ≥ 60 years, or any subject with AML regardless of age who has relapsed following a BMT.
 - Arm 2: R/R AML and age < 60 years, excluding subjects with AML who have relapsed following a BMT.
 - Arm 3: Untreated AML and age ≥ 60 years that decline standard of care chemotherapy.
 - Arm 4: IDH2-mutated advanced hematologic malignancies not eligible for Arms 1 to 3.
3. In the combined Phase 1, analyses will be presented by total daily dose groups as < 100 mg, 100 mg and > 100 mg for subjects with R/R AML. The overall subjects in the combined Phase 1 will be summarized by malignancy type including R/R AML, untreated AML, MDS, and other.
4. In Phase 2, data will be summarized primarily for all R/R AML subjects.
5. In the combined Phase 1/2, R/R AML will be presented by total daily dose groups as < 100 mg, 100 mg and > 100 mg, and the overall subjects will be presented by malignancy type.

For subjects who were discontinued from study treatment, underwent HSCT, and then re-started AG-221, data after restarting AG-221 will be excluded from all summary analyses except for death. The data collected after restarting AG-221 will be provided in listings.

Categorical variables will be summarized by frequency distributions (number and percentages of subjects) and continuous variables will be summarized by descriptive statistics (number of subjects, mean, standard deviation (SD), median, minimum, and maximum).

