6. SUBJECT DISPOSITION

The number of subjects treated, discontinued from treatment and study, along with the primary reason for discontinuation, will be summarized using frequency and percentage.

A summary of subject disposition will be presented separately for Phase 1 Dose Escalation by total daily dose, Part 1 Expansion by cohorts, and Phase 2 R/R AML, as described in items 1, 2, and 4 of [Section 5.1](#), and for the FAS analysis set.

Disposition will also be analyzed for Phase 1 Dose Escalation by assigned dose group and overall for DDS.

Subject disposition for the combined Phase 1 will be presented by malignancy type for overall subjects and by <100 mg, 100 mg, and >100 mg for R/R AML as described in item 3 of [Section 5.1](#) for the FAS analysis set.

Subject disposition for the combined Phase 1/2 will be presented by malignancy type for overall subjects and by <100 mg, 100 mg, and >100 mg and further by relapse/refractory status for R/R AML for the FAS analysis set.

Subjects screened and subjects treated by site will be summarized as described in items 1, 2, and 4 of [Section 5.1](#). A separate summary tabulation will be presented by number of subjects and the reason of screen failures for Phase 1 and Phase 2.

A by-subject data listing will be provided for subjects with reasons for screening failure. Reasons for treatment discontinuation have been collected on the electronic case report form (eCRF) and will be summarized with the following categories:

- Withdrawal of consent
- Due to AE or DLT
- Any medical condition which, in the opinion of the Investigators, would put the subject at risk for continuing treatment
- Experiences disease progression
- Development of an intercurrent medical condition or need for concomitant treatment that precludes further participation in the trial
- The Investigator removes the subject from the trial in the best interests of the subject
- Subject requires use of a prohibited concomitant medication
- Protocol violation: non-adherence to study drug regimen or protocol requirements
- Lost to follow-up
- Pregnancy
- Death
- Bone Marrow Transplant
- Other

Reasons for not completing the study follow-up/study (ie, no more follow-up visits and no longer participating in the study) have been collected on the eCRF and will be summarized for all subjects with the following categories:

- Withdrawal of consent
- Lost to follow-up
- Death
- Other

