15. APPENDICES

15.1. Handling of Dates

Dates will be stored as numeric variables in the SAS analysis files and reported in DDMMYY format (ie, the Date9. datetime format in SAS). Dates in the clinical database are classified into the categories of procedure dates, log dates, milestone dates, outcome dates, and special dates.

1. **Procedure Dates** are the dates on which given protocol-specified procedure are performed. They include the dates of laboratory testing, physical examinations, tumor scans, etc. They should be present whenever data for a protocol-specified procedure are present and should only be missing when a procedure are marked as NOT DONE in the database. Procedure dates will not be imputed.
2. **Log Dates** are dates recorded in eCRF data logs. Specifically, they are the start and end dates for AEs and concomitant medications/procedures. They should not be missing unless an event or medication is marked as *ongoing* in the database. Otherwise, incomplete log dates will be imputed according to the rules in Appendix 16.2 (eg, for duration or cycle assignment, etc). However, in listings, log dates will be shown as recorded without imputation.
3. **Milestone Dates** are dates of protocol milestones such as randomization, study drug start date, study drug termination date, study closure date, etc. They should not be missing if the milestone occurs for a subject. They will not be imputed.
4. **Outcome Dates** are dates corresponding to study endpoints such as survival, progression, etc. In most cases they are derived either from a milestone (eg, the survival date is derived from the death date), or a procedure date (eg, the progression date is derived from the date of the tumor scan that was used to determine progression). They may be subject to endpoint-specific censoring rules if the outcome did not occur, but are not otherwise subject to imputation.

Dates recorded in comment fields will not be imputed or reported in any specific format.

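### SAP 10.3.1.5 lets any dated database record set the OS censoring date, so a date that does not show the subject alive can lengthen follow-up and raise OS

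*SAP*

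**What the plan says.** Protocol 12.5.7 (Endpoints) gives the OS rule in one line: "Subjects who are alive at the analysis cutoff date will be censored at the last contact date". It leaves refinement to the SAP: "Additional details of the censoring rules will be specified in the Statistical Analysis Plan".

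SAP 10.3.1.5 has three sentences on the point. The governing one is "Subjects alive will be censored at the last date known to be alive or a pre-specified data cut-off date, whichever is earlier". The definition follows: "The last known alive date is the last non-imputed date of any subject record in the study database". Then comes a comment: "This date may be the last visit date or last contact date that the subject is known to be alive". SAP 5.1 fixes the cap, since data are analysed "up to the data cut-off date of 29 July 2019".

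Two other places show what dates the database may hold. SAP 15.1 lists milestone dates, which are not imputed, including "study drug termination date, study closure date, etc. They should not be missing if the milestone occurs for a subject". SAP 6 says: "Reasons for not completing the study follow-up/study (ie, no more follow-up visits and no longer participating in the study) have been collected on the eCRF". Loss to follow-up is one of the listed reasons.

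OS is a key secondary endpoint. It is estimated by Kaplan-Meier, with quartiles and probabilities at 3, 6, 9 and 12 months. Its only planned sensitivity analysis censors transplanted subjects at HSCT.

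**The concern.** The governing sentence in SAP 10.3.1.5 asks when the subject was last known to be alive. The definition asks only for the latest date that was not imputed. These differ whenever a subject's last dated record is administrative and not evidence of life.

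The subjects exposed are those who drop out of contact without a recorded death. If such a subject's censoring date is moved past the last evidence of life, the subject counts as under observation when a death would not have reached the database. The error has one direction only: it raises OS. There is no control arm to share it, and the one OS sensitivity analysis does not test it.

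**Working it through.** **1. The rules side by side.**

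| | Protocol 12.5.7 | SAP 10.3.1.5, governing sentence | SAP 10.3.1.5, definition |
|---|---|---|---|
| Censoring date | last contact | last known alive | latest non-imputed date on any record |
| Must show the subject alive? | in effect yes | yes | no |
| Capped at cut-off? | refers to status at cut-off | yes | yes, through the governing sentence |

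The comment after the definition is permissive. It says that the date can be a visit or contact date, and it excludes no other kind of record. The study closure date in SAP 15.1 meets the definition without showing that the subject was alive.

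**2. Direction.** The Kaplan-Meier estimate is S(t) = ∏(1 − dᵢ/nᵢ) over death times up to t. A lost subject whose censoring date is moved later is added to nᵢ in the extra interval but cannot add to dᵢ. Each affected factor rises, so S(t) can rise but not fall.

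**3. Size.** The documents state no OS median, event count or loss rate, so there is no plan figure to reproduce, and every input here is an assumption. The calculation simulated 200,000 subjects with:
- exponential survival, median 6, 9 or 12 months;
- 2%, 5%, 10% or 20% assigned a loss time uniform over 0 to 18 months (0.8% to 12.3% are actually lost before death);
- 0, 1, 3, 6 or 12 months added after last contact;
- censoring capped at administrative follow-up of 36 to 48 months.

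Check: true 12-month OS is 2^(−12/median), that is 25.0%, 39.7% and 50.0%. With nothing added the simulation gives about 25%, 40% and 50%, so censoring at the last evidence of life recovers the truth.

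| True median (months) | Assigned loss (lost before death) | Months added | Estimated median | 12-month OS, % |
|---|---|---|---|---|
| 9 | 5% (2.7%) | 3 | 9.01 → 9.07 (+0.06) | 39.6 → 39.9 (+0.3) |
| 9 | 10% (5.4%) | 6 | 9.01 → 9.26 (+0.25) | 39.6 → 40.8 (+1.2) |
| 9 | 20% (10.8%) | 12 | 9.00 → 9.66 (+0.66) | 39.6 → 43.0 (+3.4) |
| 6 | 20% (8.4%) | 12 | 6.01 → 6.29 (+0.28) | 25.1 → 28.9 (+3.8) |
| 12 | 20% (12.3%) | 12 | 11.99 → 13.18 (+1.19) | 50.0 → 52.9 (+2.9) |

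The largest shifts in the whole grid are 3.8 points at 12 months and 1.19 months in the median. Once 12 months are added, a longer gap cannot raise 12-month OS further, because every lost subject is already carried to month 12 or beyond.

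Survival contacts are scheduled every 28 days or every 3 months, so gaps of 1 to 3 months are a reasonable guess for a form completed after a missed contact. With 2% to 10% assigned to loss and those gaps, the largest shifts are +0.7 points (9-month median, 10%, 3 months: 39.6 → 40.3) and +0.21 months (12-month median, 10%, 3 months: 12.02 → 12.23).

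**4. Scale.** With 125 subjects and 12-month OS of 39.7%, an approximate standard error is √(0.397 × 0.603 / 125) = 0.044, or 4.4 points. Even the largest shift is below one standard error, but it is bias and does not average out.

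**The case against.** The strongest reply is that the paragraph should be read as a whole. Its first sentence requires the subject to be known alive, and its third ties the date to visits or contacts at which that is so. A careful programmer would leave out a closure date. This stands to the extent that the bias depends on how the definition is coded. It does not remove the conflict, because the definition is the operative sentence and contains no such limit.

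Four further points also stand, and each rules out a stronger reading that a reader might infer.

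- *That retrospective central review or loss-to-follow-up forms do extend OS.* The documents do not show this. SAP 6 says that reasons for leaving were collected but mentions no date. Nothing says that central IDH2 result dates or IRAC review dates are subject records in the study database. SAP 15.1 dates a procedure by when it was performed, so a marrow sample reviewed years later keeps its collection date. SAP 10.3.1.5 also provides for subjects with only a baseline record. That group would be largely empty in Phase 1 if retrospective test dates counted.
- *That a record of any date can count.* The cut-off already bars anything after 29 July 2019. It does not bar administrative dates before then.
- *That the SAP departs from the protocol without declaring it.* SAP 13 does not list the rule, but the protocol delegates censoring detail to the SAP and leaves last contact date undefined. The broader wording is a fault in the definition more than an undeclared change.
- *That looking beyond contacts is wrong in itself.* Samples, transfusions and the start of new therapy do show that the subject was alive, and using them is sound.

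**Conclusion.** The point holds as a defect of definition. SAP 10.3.1.5 states the right concept and then defines it by a rule that does not require evidence of life. Followed literally, that rule can carry censoring past the last such evidence and bias OS upward. The study closure date in SAP 15.1 is the best documented example. Loss-to-follow-up and central-review dates are examples only if they are recorded in the database.

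Under the assumptions stated, the shift is 0 to about 4 points in 12-month OS and 0 to about 1.2 months in the median. It is well under 1 point and about 0.2 months or less with gaps of 1 to 3 months and at most 10% assigned to loss. Whether any shift occurred cannot be told from the documents.

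A reader might take this to inflate EFS or weaken the primary result. It does neither. EFS is censored under SAP Table 3 at the last adequate response assessment, and the success criterion in SAP 10.2 rests on ORR. OS is descriptive, with no test or threshold attached. The matter is minor but cheap to correct.

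**What to change.** In SAP 10.3.1.5, define the last known alive date as the latest non-imputed date, on or before the cut-off, of a record that shows the subject alive: a visit, dose, sample collection, assessment, AE onset, transfusion, start of new therapy, or survival contact with status alive. State that study-closure, loss-to-follow-up, laboratory-result, central-review and data-entry dates do not count. Keep the existing cap at the cut-off.

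The cost is one sentence in the SAP and a small change to the derivation program. OS may become very slightly less favourable.
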